2.1. Study Rationale

The incretin hormones, glucose-dependent insulintropic polypeptide (GIP) and glucagon-like peptide-1 (GLP-1), are secreted after meal ingestion and mediate the incretin effect. Both hormones have effects on endocrine cells in the pancreas, increasing insulin biosynthesis and secretion, and modifying glucagon secretion (Skow et al. 2016). Based on these properties, several GLP-1 receptor (GLP-1R) agonists have been approved for pharmacological treatment of T2DM (Tomlinson et al. 2016).

In addition to its pancreatic effects, GLP-1R activation decreases gut motility, slows gastric emptying, and promotes satiety (presumably through a combination of GLP-1R activation in the central and peripheral nervous systems), thereby regulating food intake and body weight (Baggio and Drucker 2007). The US FDA and the European Medicines Agency (EMA) approved the GLP-1R agonist liraglutide for the treatment of overweight and obesity (SAXENDA package insert, 2014; SAXENDA summary of product characteristics 2015).

Preclinical data indicate that GIP also exerts effects on appetite regulation and food intake, on adipose tissue, and on peripheral energy metabolism. Although studies evaluating effects of GIP

on body weight have yielded equivocal results, GIP receptor (GIPR) activation may play a role in body weight regulation and targeting both the GLP-1R and the GIPR simultaneously could potentially result in additive or synergistic effects of the 2 incretins on body weight (Coskun et al. 2018).

CCI

It is administered once-weekly (QW) by subcutaneous (SC) injection. As a dual GIP/GLP-1R agonist, tirzepatide could exceed the efficacy of selective GLP-1R agonists by recruiting metabolically active tissues not targeted by selective GLP-1R agonists (for example, adipose tissue as indicated by the observation of increased energy utilization) (Müller et al. 2018) and has the potential to reach higher efficacy in target tissues that express both GIPR and GLP-1R. Therefore, tirzepatide has the potential to impact several aspects of energy regulation and be a treatment for overweight and obesity.

Compared to people without diabetes, patients with T2DM and obesity or overweight often respond less favorably to weight-management treatments (Pi-Sunyer, 2005) and may face unique safety issues such as risk for hypoglycemia following weight loss, if the dose of certain background medications for the management of hyperglycemia is not appropriately adjusted. Therefore, it is important to conduct a dedicated phase 3, randomized, double-blind, placebo-controlled study in patients with T2DM and obesity or overweight to evaluate the efficacy and safety of novel chronic weight management products. In addition, weight loss should be demonstrated over the course of at least 1 year before a product can be considered as effective for weight management (FDA 2007).

Study 18F-MC-GPHL is a Phase 3, multicenter, randomized, parallel, placebo-controlled, double-blinded study that will investigate the effects of treatment with tirzepatide 10 mg and 15 mg QW compared with placebo, in conjunction with a reduced-calorie diet and increased physical activity, on weight management at 72 weeks in participants with T2DM who have obesity or are overweight.

2.2. Background

There remains an unmet need in the pharmacologic treatment of obesity for drugs that are safe, efficacious, and well-tolerated. There are currently only a few medications FDA-approved for long-term use for the treatment of obesity that yield a placebo-adjusted average weight loss between 3% and 7% (Srivastava and Apovian 2018b, FDA 2020). Although moderate weight loss of 5% to 10% in individuals with obesity/overweight has long been shown to yield significant metabolic benefits including improvements in cholesterol, blood pressure, and glucose parameters (Goldstein 1992; Wing et al. 2011), greater weight loss can maximize these benefits and may be required to realize clinically meaningful improvements in other obesity-related comorbidities such as sleep apnea, nonalcoholic steatohepatitis, and cardiovascular disease (Ryan et al. 2017). In addition to moderate efficacy, some centrally-acting weight loss agents to-date have had adverse neurocognitive, psychiatric, or cardiovascular effects, further limiting their application in clinical practice (Srivastava and Apovian 2018b).

Weight loss induced by GLP-1R agonists, while appearing to be centrally-mediated through a combination of hormonal inputs to satiety centers (van Bloemendaal et al. 2014), has not been consistently associated with changes in mental health or with potential for addiction in long-term

studies conducted to establish cardiovascular safety in patients with diabetes (Marso et al. 2016a, 2016b; Gerstein et al. 2019). Tirzepatide, which is both a GLP-1R and GIPR agonist, has been associated with predominantly mild to moderate GI adverse effects similar to currently marketed GLP-1R agonists, but has also demonstrated significant weight loss at both the 10 mg and 15 mg doses in Phase 2 studies with nearly half of the participants in both dose arms achieving $\geq 10\%$ weight loss (Frias et al. 2018).

Dose selection for obesity treatment has been informed by 3 clinical trials: a Phase 1 study, Study I8F-MC-GPGA (GPGA), and 2 Phase 2 studies, Study I8F-MC-GPGB (GPGB) and I8F-MC-GPGF (GPGF).

Phase 1 Study GPGA was a combination of single ascending dose (SAD) and multiple ascending dose (MAD) study in healthy subjects followed by a multiple dose study in patients with T2DM. A total of 142 participants (89 healthy subjects and 53 patients with T2DM) received at least 1 dose of treatment. Doses of tirzepatide ranged from:

- 0.25 mg to 8 mg in the SAD (with maximum tolerated dose achieved at 5 mg) in healthy subjects,
- multiple doses in the MAD from 0.5 mg to 4.5 mg QW and titrated doses up to 10 mg QW for 4 weeks in healthy subjects, and
- multiple doses at 0.5 mg and 5 mg QW and titrated to 15 mg QW for 4 weeks in patients with T2DM.

The safety and tolerability and pharmacokinetic/pharmacodynamic (PK/PD) profiles of tirzepatide at doses and escalation regimens administered in this Phase 1 study supported further development of tirzepatide for QW dosing in patients with T2DM.

Phase 2 studies I8F-MC-GPGB (GPGB) and I8F-MC-GPGF (GPGF) provided initial safety, tolerability, and efficacy data in the tirzepatide 1 to 15 mg dose-range when used in treatment of patients with T2DM. In the dose range of 5 to 15 mg, tirzepatide provided significantly greater reductions in HbA1c and body weight compared with placebo. In addition, 10-mg and 15-mg dose arms demonstrated significantly greater weight loss compared to the GLP-1R agonist dulaglutide 1.5 mg QW. The most common adverse events (AEs), which were also dose dependent, were mild to moderate nausea, vomiting, and diarrhea. Study GPGF showed that adjustments in the tirzepatide dose escalation algorithm resulted in additional reductions in the frequency of GI AEs and reduced the frequency of treatment discontinuations due to GI AEs.

2.3. Benefit/Risk Assessment

More detailed information about the known and expected benefits and risks and reasonably expected AEs of tirzepatide may be found in the Investigator's Brochure (IB).

3. Objectives and Endpoints

Objectives	Endpoints
Primary	

To demonstrate that tirzepatide 10 mg QW is superior to placebo at 72 weeks for:
 
 • Percent change in body weight AND • Proportion of participants with $\geq 5\%$ body weight reduction 
AND/OR
 
To demonstrate that tirzepatide 15 mg QW is superior to placebo at 72 weeks for:
 
 • Percent change in body weight AND • Proportion of participants with $\geq 5\%$ body weight reduction 	
 • Mean percent change in body weight from randomization • Percentage of study participants who achieve $\geq 5\%$ body weight reduction from randomization
Key Secondary (controlled for type I error), by dose analysis	

For QW tirzepatide 10 mg and/or 15 mg doses, to demonstrate superiority to placebo in change from randomization for the following (measured at 72 weeks):
 
 • Body weight • Glycemic control • Waist circumference 	
 • Percentage of participants who achieve: 
 ○ $\geq 10\%$ body weight reduction ○ $\geq 15\%$ body weight reduction • Mean change in HbA1c (%) • Percentage of participants who achieve HbA1c $< 7\%$ • Mean change in fasting glucose (mg/dL) • Mean change in waist circumference (cm)
Key secondary (controlled for type I error), pooled dose analysis	

For QW tirzepatide (all doses combined) to demonstrate superiority to placebo in change from randomization for the following (measured at 72 weeks):
 
 • Lipid parameters • SBP 	
 • Mean change in fasting 
 ○ Total cholesterol (mg/dL) ○ LDL-cholesterol (mg/dL) ○ Triglycerides (mg/dL) • Mean change in SBP (mmHg)

Additional Secondary, by dose analysis
	

For QW tirzepatide 10 mg and/or 15 mg doses, to demonstrate superiority to placebo in change from randomization for the following (measured at 72 weeks):
 
 • Body weight • Glycemic control • Insulin • Patient-Reported Outcomes 	
 • Mean change in absolute body weight (kg) • Mean change in BMI (kg/m²) • Percentage of study participants who achieve HbA1c ≤6.5% • Percentage of study participants who achieve HbA1c <5.7% • Mean change in fasting insulin (pmol/L) • Mean change in 
 ○ SF-36v2 acute form Physical Functioning domain score ○ IWQOL-Lite-CT Physical Function composite score

Additional Secondary, pooled analysis
	

4. Study Design

4.1. Overall Design

Study 18F-MC-GPHL is a Phase 3, multicenter, randomized, parallel, placebo-controlled, double-blinded, 72-week study that will investigate the safety and efficacy of treatment with tirzepatide 10 mg and 15 mg QW SC compared with placebo QW SC, in conjunction with a reduced-calorie diet and increased physical activity, on weight management in participants with T2DM who have obesity (body mass index [BMI] ≥ 30 kg/m²) or are overweight (BMI ≥ 27 kg/m²).

Study participants will be randomized in a 1:1:1 ratio (tirzepatide 10 mg QW, tirzepatide 15 mg QW, and placebo). An upper limit of 70% enrollment of women will be used to ensure a sufficiently large sample of men. In addition, an upper limit of 30% enrollment of participants treated with SU will be used to allow sufficient enrollment of participants treated with other antihyperglycemic medications (AHMs).

All participants will undergo a 3-week screening period, a 72-week treatment period (including a 20-week dose escalation and a 52-week dose maintenance period), and a 4-week safety follow-up period.

4.1.1. Overview of Study Periods

4.1.1.1. Visit Structure for all Office Visits

On all office visits (other than Visit 2), study participants are required to report to the site in a fasting condition, after a period of approximately 8 hours without eating, drinking (except water), or performing any significant physical activity and before taking study drug(s). The participant should not take any AHMs prior to the visit. If participants are adversely affected by the fasting condition, they are allowed to eat; however, specific study procedures need to be completed while fasting. See Section 10.8 Appendix 8 for a suggested order of activities that occurs at office visits.

4.1.1.2. Main Study Period

4.1.1.2.1. Screening Period

Visit 1

The purpose of screening procedures at Visit 1 is to establish initial eligibility and to obtain blood samples for laboratory assessments needed to confirm eligibility. The participant must sign the informed consent form (ICF) before the study procedures are performed, as outlined in the Schedule of Activities (SoA), Section 1.3. Since some screening procedures need to be completed in the fasting state (approximately 8 hours without eating, drinking [except water], or any significant physical activity), Visit 1 may be conducted over more than 1 day to ensure necessary conditions are met.

Patient-reported outcomes (PROs) questionnaires should be administered as early as possible, as per Suggested Visit Structure (Section 10.8). Preferred recommended administration order is:

1. Patient Global Impression of status for physical activity (PGIs)
2. Short Form-36 version 2 Health Survey acute form (SF-36v2 acute form)
3. Impact of Weight on Quality of Life-Lite-Clinical Trials Version (IWQOL-Lite-CT)

Participants who meet all applicable inclusion criteria and none of the applicable exclusion criteria at Visit 1 will continue to Visit 2.

Visit 2

At Visit 2, the screening laboratory results will be reviewed. For all participants who remain eligible after Visit 1, a dilated fundoscopic examination will be performed by an eye care professional (ophthalmologist or optometrist) between Visit 2 and Visit 3 to exclude participants with proliferative diabetic retinopathy, diabetic macular edema, or nonproliferative diabetic retinopathy that requires acute treatment.

Participants will be provided diaries and be trained to record key study information, as appropriate.

Diabetes education will be performed by personnel who are qualified to educate participants on symptoms and management of hyperglycemia and hypoglycemia, self-monitored BG, self-injection and diabetes management according to American Diabetes Association Standards of Medical Care in Diabetes (ADA 2020) or local standards. Participants will be trained on how to utilize BG meters and how to collect self-monitoring of blood glucose (SMBG), including 7-point measurements as appropriate. Blood glucose meters/supplies will be provided to measure SMBG values and participants will be required to record them in the study diary.

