1.3. Schedule of Activities (SoA)

The Schedule of Activities described below should be followed for all participants enrolled in Study GPHL. However, for those participants whose participation in this study is affected by exceptional circumstances (such as pandemics or natural disasters), please refer to Section 10.11 Appendix 11 for additional guidance.

Visit	1	2	3	4	5	6	7	8	9	10	11	12	13	14	15	16	17	18	19	20	21	99	ED	801
Week of Treatment	-3	-2	0	4	8	12	16	20	24	28	32	36	40	44	48	52	56	60	64	68	72	72		4 wks post end of TxP
Allowable Interval Tolerance (days)		±3	±7	±3	+7	±3	+7	±3	±3	±3	±3	+7	±3	±3	±3	±3	±3	±3	±3	±3	±7	±7		±3
Fasting Visit	X		X	X	X	X	X	X	X			X			X			X			X	X	X	X
Telephone Visit										X	X		X	X		X	X		X	X				
Informed consent	X																							
Inclusion and exclusion criteria review	X	X	X																					
Preexisting conditions and medical history, including relevant surgical history	X																							
	Medical history includes assessment of preexisting conditions (for example, history of gallbladder disease, cardiovascular disease, and medullary thyroid carcinoma) and substance usage (such as alcohol and tobacco).																							
Concomitant medications	X	X	X	X	X	X	X	X	X	X	X	X	X	X	X	X	X	X	X	X	X	X	X	X
Adverse events and product complaints	X	X	X	X	X	X	X	X	X	X	X	X	X	X	X	X	X	X	X	X	X	X	X	X
Physical Evaluation or Clinical Assessments																								
Height	X																							
Weight	X		X	X	X	X	X	X	X			X			X			X			X	X	X	X
	Weight measurements should be obtained per the detailed protocol guidance in Section 10.7. Body weight must be measured in the fasting state. If the participant is not fasting, the participant should be called in for a new visit within the visit window to have the fasting body weight measured.																							
Waist circumference			X	X	X	X	X	X	X			X			X			X			X	X	X	X
Vital signs (systolic and diastolic blood pressure, pulse rate)	X		X	X	X	X	X	X	X			X			X			X			X		X	X
	Vital sign measurements should be taken before obtaining an ECG tracing and before collection of blood samples for laboratory testing, per the instruction in Section 10.7.																							

Visit	1	2	3	4	5	6	7	8	9	10	11	12	13	14	15	16	17	18	19	20	21	99	ED	801
Week of Treatment	-3	-2	0	4	8	12	16	20	24	28	32	36	40	44	48	52	56	60	64	68	72	72		4 wks post end of TxP
Allowable Interval Tolerance (days)		±3	±7	±3	+7	±3	+7	±3	±3	±3	±3	+7	±3	±3	±3	±3	±3	±3	±3	±3	±7	±7		±3

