9.2. Sample Size Determination

Approximately 1300 participants will be screened to achieve 900 randomly assigned to study intervention (300 participants per intervention group).

The sample size determination assumes that evaluation of superiority of tirzepatide 10 mg and tirzepatide 15 mg to placebo will be conducted in parallel, each at a 2-sided significance level of 0.025 using a 2-sample t-test. Additionally, a difference of at least 11% mean body weight percentage reduction from randomization at 72 weeks for tirzepatide 10 mg and/or tirzepatide 15 mg compared to placebo, a common SD of 10%, and a dropout rate of 25% are assumed for statistical power calculations. Under the assumptions above, randomizing 900 participants in a 1:1:1 ratio to tirzepatide 10 mg (300), tirzepatide 15 mg (300), and placebo (300) provides more than 90% power to demonstrate superiority of each tirzepatide dose to placebo.

The chosen sample size and randomization ratio also provides >90% power to establish superiority of 10 mg tirzepatide and 15 mg tirzepatide dose to placebo in terms of proportion of participants achieving at least 5% body weight reduction at 72 weeks, conducted in parallel using a Chi-square test, each at a 2-sided significance level of 0.025, assuming 25% placebo treated participants and 90% tirzepatide treated participants achieving the goal and a dropout rate of 25%.

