4.1. General Considerations

Statistical analysis of this study will be the responsibility of Lilly or its designee. Some analyses and summaries described in this analysis plan may not be conducted if not warranted by data (eg, few events to justify conducting an analysis). Additional analyses of the data may be conducted as deemed appropriate.

Unless otherwise noted, tests of treatment effects will be conducted at a 2-sided alpha level of 0.05, and the CI will be calculated at 95% 2-sided.

Unless specified otherwise, efficacy and safety will be assessed using the mITT population, and data will be analyzed based on the assigned treatment (ie, not the actual treatment received by the participant).

Summary descriptive statistics for continuous measures will include sample size, mean, SD, median, minimum, and maximum. The analysis model to make comparisons among treatment groups relative to continuous measurements assessed over time will be either ANCOVA or a MMRM.

Kaplan-Meier method will be used for estimation of cumulative event-free survival rates over time, and Cox proportional hazards regression analysis will be used to compare hazards rates among treatments.

Summary statistics for categorical measures (including categorized continuous measures) will include sample size, frequency, and percentages. Logistic regression will be used to examine the treatment difference in binary efficacy outcomes if there is a need to adjust for covariate. Otherwise, Fisher's exact test will be used to examine the treatment difference.

Summary statistics for discrete count measures will include sample size, mean, SD, median, minimum, and maximum.

Unless specified otherwise, baseline will be defined as the last available nonmissing measurement during Visit 1 to Visit 3. For the safety-related parameters, the definition of baseline and postbaseline are specified in [Table GPHL.4.1](#).

Table GPHL.4.1. Baseline and Postbaseline Definitions for Safety Groups

Analysis Set	Analysis Type	Baseline	Postbaseline
SS	(1.1) Treatment-Emergent Adverse Events	The baseline period is defined as the start of screening and ends prior to the first dose of study treatment (typically at Week 0).	Starts after the first dose of study treatment and ends at the end of the study period (including off-drug follow up visit).

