4.4. Secondary Endpoint(s)/Estimands(s) Analysis

4.4.1. Key Secondary Analyses Subject to Type 1 Error Rate Control

Table GPHL.4.2. Key Secondary Measures (Controlled for Type 1 Error)

Objectives	Relative to the efficacy measure:	Analysis conducted in a manner similar to	Additional Information
Tirzepatide 10 mg and/or 15 mg is superior to placebo:	Percentage of participants achieving body weight reduction $\geq 10\%$, $\geq 15\%$ and $\geq 20\%$ at 72 weeks	logistic model in Section 4.3.2.1 for treatment-regimen estimand and logistic model in Section 4.3.2.2 for efficacy estimand	
	Mean change in HbA1c (%) from randomization at 72 weeks	ANCOVA model in Section 4.3.2.1 for treatment-regimen estimand and MMRM model in Section 4.3.2.2 for efficacy estimand, with baseline HbA1c value to replace baseline body weight as an additional covariate.	LSM estimates will be plotted by treatment through 72 weeks.
	Percentage of participants achieving target value of HbA1c $< 7\%$, $\leq 6.5\%$ and $< 5.7\%$ at 72 weeks	logistic model in Section 4.3.2.1 for treatment-regimen estimand and logistic model in Section 4.3.2.2 for efficacy estimand, with baseline HbA1c value to replace baseline body weight as an additional covariate.	
	Mean change in waist circumference (cm) from randomization at 72 weeks	ANCOVA model in Section 4.3.2.1 for treatment-regimen estimand and MMRM model in Section 4.3.2.2 for efficacy estimand, with baseline waist circumference to replace baseline body weight as an additional covariate.	LSM estimates will be plotted by treatment through 72 weeks.
	Mean change in fasting glucose (mg/dL) from randomization at 72 weeks	ANCOVA model in Section 4.3.2.1 for treatment-regimen estimand and MMRM model in Section 4.3.2.2 for efficacy estimand	Baseline fasting glucose will be used a covariate and baseline HbA1c group ($\leq 8.5\%$, $> 8.5\%$) will be used as a fixed effect. LSM estimates will be plotted by treatment through 72 weeks.
Tirzepatide (all doses combined) is superior to placebo:	Mean change in triglycerides, HDL-cholesterol, and non-HDL-cholesterol from randomization at 72 weeks	ANCOVA model in Section 4.3.2.1 for treatment-regimen estimand and MMRM model in Section 4.3.2.2 for efficacy estimand, with baseline lipids value in place of baseline body weight as a covariate.	Estimated means will be plotted by treatment through 72 weeks. Log transformation will be adopted for lipid parameters.

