Objectives	Relative to the efficacy measure:	Analysis conducted in a manner similar to	Additional Information
	Mean change in SBP (mmHg) from randomization at 72 weeks	ANCOVA model in Section 4.3.2.1 for treatment-regimen estimand and MMRM model in Section 4.3.2.2 for efficacy estimand, with baseline SBP in place of baseline body weight as a covariate.	LSM estimates will be plotted by treatment through 72-weeks.

Abbreviations: ANCOVA = analysis of covariance; HbA1c = hemoglobin A1c; HDL = high-density lipoprotein; LSM = least squares mean; MMRM = mixed model for repeated measures; SBP = systolic blood pressure.

Decision regarding reject/accept of the statistical hypothesis for each objective will be guided by the 2-sided p-values, and details are included in Section 2.1.

For submission of Study GPHL to the US FDA to support the registration of tirzepatide for chronic weight management, the key secondary efficacy assessment will be guided by the treatment regimen estimand, conducted using the same population as for the primary analysis. Assessment of the key secondary objectives will be conducted with hybrid imputation of missing data (see Section 4.3.2.3).

For other regulatory agencies, publications, and other purposes, the assessment of key secondary efficacy objectives may be guided by the efficacy estimand using the same population as for primary analysis.

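### Free improvement: blood pressure, fasting glucose, lipids and two patient-reported outcomes are measured at both Visit 1 and Visit 3 before treatment, but the efficacy models adjust only for the last value; adding Visit 1 as a second covariate gives a modest gain in precision

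*Protocol*

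**What the plan says.** Protocol Section 4.1.1.2.1 gives the role of Visit 1: "The purpose of screening procedures at Visit 1 is to establish initial eligibility and to obtain blood samples for laboratory assessments". The Schedule of Activities (Protocol Section 1.3) marks the row "Vital signs (systolic and diastolic blood pressure, pulse rate") at Visit 1 (Week -3) and Visit 3 (Week 0). It does the same for the chemistry panel with glucose, the lipid panel, free fatty acids, SF-36v2 and IWQOL-Lite-CT. Both are fasting visits, and the first dose comes at the end of Visit 3.

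SAP Section 4.1 states that "baseline will be defined as the last available nonmissing measurement during Visit 1 to Visit 3"; Protocol Section 9.4.1 agrees in substance. Table GPHL.4.2 then specifies the lipid models "with baseline lipids value in place of baseline body weight as a covariate" and the SBP model "with baseline SBP in place of baseline body weight as a covariate". The fasting glucose model has one baseline glucose value plus baseline HbA1c group. In Table GPHL.4.3 the SF-36v2 and IWQOL-Lite-CT models each have one baseline score. DBP, free fatty acids and the remaining lipids are referred to the MMRM of Section 4.3.2.2, with no own-baseline covariate named in the table. All models also carry country, sex and type of antihyperglycemic medication.

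**The concern.** These outcomes fluctuate within a person, so one pre-treatment reading is a noisy measure of the usual level. A second reading, taken about three weeks earlier on everyone, can explain some of the Week 72 variance that the first leaves. Both readings precede randomization, so using both cannot bias the comparison, and the change score and the estimand stay as they are.

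SBP, triglycerides, HDL cholesterol, non-HDL cholesterol and fasting glucose are key secondary endpoints under type I error control. SF-36v2 and IWQOL-Lite-CT physical function, DBP, free fatty acids and the other lipids are additional secondary endpoints. The sample size sections state power only for the two weight endpoints. What is at stake is the width of these secondary confidence intervals.

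**Working it through.** **The plan's own figure.** Protocol Section 9.2 tests each dose "each at a 2-sided significance level of 0.025 using a 2-sample t-test", assumes "a difference of at least 11% mean body weight percentage reduction from randomization at 72 weeks", and adds "a common SD of 10%, and a dropout rate of 25% are assumed for statistical power calculations". With 300 × 0.75 = 225 per arm, the noncentrality is (11/10) × √(225/2) = 11.7 against a critical value of about 2.25, so power exceeds 0.999. The chi-square comparison of 25% with 90% also exceeds 0.999. The stated power of more than 90% is reproduced. About 21 per arm (28 with dropout) would give 90% for the mean difference, so the primary endpoints have nothing to gain here.

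**Formula.** Let r3 and r1 be the correlations of the Visit 3 and Visit 1 values with Week 72, and rb the correlation between the two visits. None is in the documents; all values below are assumptions.

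- Residual variance factor, Visit 3 only: 1 − r3².
- Both as covariates: 1 − (r1² + r3² − 2·r1·r3·rb)/(1 − rb²).
- Relative variance reduction: (r1 − r3·rb)² / [(1 − rb²)(1 − r3²)].

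Example, SBP with r3 = r1 = 0.40 and rb = 0.60: (0.40 − 0.24)² / (0.64 × 0.84) = 0.0256/0.5376 = 4.8%. If r1 is 0.30: (0.30 − 0.24)²/0.5376 = 0.7%.

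| Outcome (r3, rb) | r1 = r3 | r1 = r3 − 0.05 | r1 = r3 − 0.10 |
|---|---|---|---|
| SBP (0.40, 0.60) | 4.8% | 2.3% | 0.7% |
| SBP (0.55, 0.65) | 9.2% | 5.0% | 2.1% |
| Log triglycerides (0.60, 0.75) | 8.0% | 3.6% | 0.9% |
| SF-36 physical functioning (0.60, 0.80) | 6.3% | 2.1% | 0.2% |
| Fasting glucose (0.35, 0.70) | 2.5% | 0.7% | 0.0% |

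If r1 = r3·rb, Visit 1 adds nothing and the reduction is exactly zero.

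**Check by simulation, complete data.** ANCOVA with 225 placebo and 450 pooled tirzepatide participants gave variance ratios of 0.934 at (rf 0.45, rb 0.60) and 0.905 at (0.55, 0.65), where rf is the common value of r1 and r3. The formula gives 0.937 and 0.908. The estimates were unbiased.

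**What this means for an interval.** SBP at r1 = r3: 1 − √0.952 = 2.4% and 1 − √0.908 = 4.7% narrower. A test with 80% power at two-sided 0.05 would rise to about 82% to 83% with a variance reduction of 6% to 8%.

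**Covariate or average.** At r3 = 0.50, rb = 0.70 and r1 = 0.35 (= 0.50 × 0.70), two covariates gain 0%. The mean of the two visits explains (0.35 + 0.50)²/(2 × 1.70) = 0.2125, leaving 0.7875 against 0.75, which is 5.0% worse. Two covariates are the safer form.

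**Planned imputation.** The treatment-regimen analysis of the key secondary endpoints imputes missing Week 72 values from retrieved dropouts in the same arm (SAP Section 4.3.2.3). A simulation assumed 25% missing, 10% retrieved and r1 = r3 at the two SBP settings. The gain was about 0% to 1% with Visit 1 in the analysis model only, and about 1% to 4% with it in the imputation model as well. These figures can move by a point or two with the number of retrieved dropouts and other set-up choices, so they are orders of magnitude.

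**The case against.** The strongest reply is that this is a preference and not a defect. The last value before treatment is a standard baseline, and the protocol and SAP agree on it. That stands: a reader might infer bias or an inconsistency, and the documents show neither.

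It would also be too strong to say that Visit 1 data are discarded, or that the last value is the only adjustment. Visit 1 labs and vital signs enter the safety baseline for treatment-emergent abnormalities (Table GPHL.4.1). The models also have the stratification factors and, for glucose, HbA1c group. Blood pressure is taken twice per visit (Protocol Section 10.7), and SAP Section 4.6.3.4, in the safety analyses, averages same-visit readings. These features trim the gain, and the formula above does not count them.

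The second reply is about size, and it largely stands. The upper figures need Visit 1 to predict Week 72 as well as Visit 3 does. Visit 1 is earlier, and Protocol Section 10.11 allows up to 90 days between the visits in exceptional circumstances. A modest drop in r1 removes most of the gain, and so does the planned imputation if Visit 1 is left out of it.

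A reader might turn 4.8% to 9.2% for SBP into about 5% to 10% more participants, or 45 to 90 of 900. The documents do not support that. It requires r1 = r3, complete Week 72 data and all 900 analysed, whereas the plan itself assumes 25% dropout.

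None of this makes the change harmful. Stable therapy is required for three months before screening, and diet counselling, secretagogue reduction and study drug all begin at Visit 3. It is therefore reasonable, though not certain, that Visit 1 carries some extra information.

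**Conclusion.** The point holds as a free improvement of modest and uncertain size. The schedule and the last-value rule are as described, and a second pre-randomization covariate costs about one degree of freedom without bias or change of estimand.

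With complete data, the variance reduction is about 0.7% to 9% for SBP, 0.9% to 8% for triglycerides, 0.2% to 6% for SF-36 physical functioning and 0% to 2.5% for fasting glucose, over the assumed correlations. It is zero if Visit 1 adds nothing beyond Visit 3. Under the retrieved-dropout imputation, about 1% to 4% for SBP is realistic even with equal prediction, and only if the imputation model also uses Visit 1. No figure was derived for the MMRM or for HDL cholesterol, non-HDL cholesterol, DBP, free fatty acids or IWQOL-Lite-CT; for these only the direction is claimed.

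The primary endpoints are unaffected. Waist circumference, fasting insulin and EQ-5D-5L have no Visit 1 value, so the point does not reach them. Body weight and HbA1c are also measured at both visits, but no change to their models is proposed.

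**What to change.** Keep baseline and change from baseline as the SAP defines them. Then amend the SAP, before unblinding, as follows.

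- **Tables GPHL.4.2 and GPHL.4.3:** add the Visit 1 value as a second covariate in the ANCOVA and MMRM for SBP, DBP, fasting glucose, the lipids including free fatty acids, SF-36v2 and IWQOL-Lite-CT. Use the log scale where the outcome is logged. Do not average the two visits. For DBP, free fatty acids and the additional lipids, name the own-baseline covariate explicitly at the same time.
- **Section 4.3.2.3:** for the key secondary endpoints in this list, include the Visit 1 value in the imputation model where the number of retrieved dropouts allows. With few of them, the extra parameter can cancel the gain.
- **Missing values:** if either the Visit 1 or the Visit 3 value is missing, use the available value for both covariates.

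The cost is SAP wording and about one degree of freedom per model, with no new data. Protocol Section 9.4.1 allows changes of method that do not alter a principal feature to be made in the SAP without a protocol amendment.
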